4.7.2 Other Safety Variables

All incidents captured in the study will be listed in [Listing 16.2.7.3](#).

4.8 Analysis of Other Variables

There will be ten subjects selected for repeated MLSI assessments to test the consistency of the examiner. .

The repeat MLSI area and intensity assessments will be cross tabulated ([Table 14.2.5.1](#) and [Table 14.2.5.2](#)) and compared to the original assessments and will not be used in any efficacy analysis. A weighted Kappa coefficient (κ), along with the 95% CI will be calculated to assess the intra-examiner reliability. Fleiss-Cohen weighted kappa will be calculated for the repeatability analysis. Reliability will be deemed

- Excellent if $\kappa > 0.75$
- Fair to good if $0.4 \leq \kappa \leq 0.75$
- Poor if $\kappa < 0.4$

All subjects who have repeatability data will be included in this analysis.

5 Changes to the Protocol Defined Statistical Analysis Plan

There is an additional analysis to the originally planned statistical analysis specified in the [protocol version 5.0 \[\(Dated: 30/May/2017\)\]](#). This additional analysis is the repeatability analysis described in Section 4.7.

6 References

Lobene RR. Effect of Dentifrices on Tooth Stains with Controlled Brushing. *Journal of American Dentistry* 1968: 77; 849-855.

[figure not shown]
CCI

207872

Statistical Reporting and Analysis plan, 24 Aug 2017

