Stain assessments will be made on the facial and lingual surfaces of the anterior teeth as these surfaces are considered the most aesthetically important with respect to dental stain accumulation. Dental stain largely builds up in the harder to reach interproximal areas, therefore in addition to analysis of the total MLSI (A×I) the interproximal regions have also been given focus as an exploratory objective in this study. As most of the stain is removed from the body and gingival regions, we would expect to see little change in the total gingival MLSI (A×I) and total body MLSI (A×I), therefore, these variables are not being analysed in this study. Furthermore, separate analysis of the facial and lingual surfaces are not of focus in this study. As the facial teeth are the most brushed we would expect to see little stain build up on the facial surfaces in comparison to the lingual surfaces, with little difference expected between the total MLSI (A×I) and total lingual MLSI (A×I).

A single examiner will perform the dental stain assessments for all subjects at the baseline, Week 2 and 4 visits to avoid inter-examiner variability. To assess the repeatability of the stain assessments 30 repeat examinations will be performed by the dental examiner over the duration of the study.

The dosage regimen of twice daily use (morning and evening) will be the same for all subjects, and has been selected based on widely recommended oral hygiene practice, and typical consumer habit.

Document Name	207872 Clinical Protocol.doc		
Type	Version	Document Identifier	Effective Date
elido_clinical_doc	5.0; Most-Recent; Effective; CURRENT	090032d580d488e0	30-May-2017 04:37:09
Reason For Issue	Auto Issue		

Sensodyne Complete Protection has been selected as a reference dentifrice in this study as it is a commercialised SnF₂ containing dentifrice. Colgate Cavity Protection® has been selected as a reference comparator as it is marketed globally, does not contain any ingredients known to impart extrinsic dental stain, and is considered to be representative of a moderate abrasivity standard, daily use fluoride dentifrice. Two recent stain build up studies have been conducted by GSKCH, which contain both the commercialised SnF₂ dentifrice and Colgate Cavity Protection®, providing us with a recent benchmark of relative and expected performance at the Week 4 time-point.

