1.1 Study Design

This is a single-centre, examiner-blind, randomised, four treatment, parallel group study, stratified by baseline total MLSI (A×I) score for the facial surfaces of at least 11 of the 12 anterior teeth (<45 (low); ≥45 (high)) and smoking status (smoker; non smoker). A single dental examiner will perform a full MLSI assessment of the area and intensity of extrinsic dental stain on the facial surfaces of the 6 maxillary and 6 mandibular anterior teeth (universal numbering: 6-11 and 22-27), and the lingual surfaces of the 6 mandibular anterior teeth (universal numbering: 22-27), at baseline (Visit 2), and following 2 and 4 weeks twice daily brushing (Visits 3 and 4).

Potential subjects will be pre-screened via telephone and later attend a screening visit during which they will give their written informed consent to participate in the study. Demography, medical history and concomitant medications will be recorded, followed by an oral examination. This will include an oral soft tissue (OST) examination, a full oral hard tissue (OHT) examination and a visual MLSI stain assessment. Subjects deemed (in the opinion of the examiner) to have a sufficient level of extrinsic dental staining (assessed to be formed due to ingestion of food or drinks, or use of tobacco products) on the facial surfaces of the scorable anterior (maxillary and mandibular) teeth, as well as meeting all other study criteria, will be considered as eligible to proceed with the study. Eligible subjects will continue to use

their own dentifrice at home until their baseline visit. Prior to the baseline visit, subjects will be asked to abstain from oral hygiene for at least 6 hours.

At baseline, each subject will undergo an OST and a full OHT, and then brush their anterior teeth for 30 seconds using a wetted toothbrush (with tap water), prior to undergoing a full MLSI stain assessment. Subjects with a sufficient level of extrinsic dental stain (in the opinion of the examiner) on the facial surfaces of the scorable anterior (maxillary and mandibular) teeth, who continue to meet all study criteria, will be stratified (based on pre-prophylaxis baseline total MLSI (A×I) score and smoking status) and randomised to treatment. The stratification factor will give rise to four strata:

- MLSI Score High (≥ 45), Smoker
- MLSI Score Low (< 45), Smoker
- MLSI Score High (≥ 45), Non Smoker
- MLSI Score Low (< 45), Non Smoker

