A dental hygienist will professionally clean each subject's teeth using a conventional dental prophylaxis paste followed by flossing (carried out by the hygienist) to remove all visible stain, plaque, debris, and all sub- and supra-gingival calculus from the anterior teeth. A second dental examiner will confirm all sub- and supra-gingival calculus, visible stain (Total MLSI (A×I) = 0), plaque and debris has been removed from the facial, palatal/lingual surfaces of the anterior teeth (visually and by tactile assessment using a dental explorer). Subjects will then be requested to brush twice daily (morning and evening) with their allocated study dentifrice for the next 4 weeks. They will receive verbal and written product usage instructions. First product use will be supervised on site, with a further supervised brushing at Visit 3. Subjects will be asked to record each product use in a diary, and note any significant changes to diet or smoking status, medications and health during the course of the study, and confirmed by the site at each visit.

Subjects will return to the site at Visits 3 and 4, having abstained from oral hygiene for at least 6 hours prior to their visit. Subjects will brush their anterior teeth for 30 seconds using a wetted toothbrush, prior to undergoing a full MLSI stain assessment. Subjects will be asked to bring their study dentifrice, toothbrush and completed diary card to each visit to facilitate compliance checks.

Randomised subjects who request so will be offered a full mouth dental prophylaxis on completion of Visit 4 procedures, or on completion of the visit where they exit the study.

Repeat examinations will be performed by the dental examiner at each full MLSI assessment visit. Ten subjects will be randomly selected for repeat examinations across each assessment window (a total of 30 repeat examinations over the duration of the study) at Visits 2 (pre-prophylaxis), 3 and 4. There will be a minimum of 10 minutes, and a maximum of 30 minutes between repeatability examinations.

Study Schedule

Procedure	Pre-screening	Visit 1 Screening	Visit 2 Baseline (Day0)	Visit 3 Week 2 (Day14 ± 2)	Visit 4 Week 4 (Day28 ± 2)
Telephone Screening of Subjects	✓				
Inform Consent		✓			
Demographics, Medical History, Smoking Status		✓			
Current / Concomitant Medication		✓	✓	✓	✓
Oral Soft Tissue (OST) Examination		✓	✓		
Full Oral Hard Tissue (OHT) Examination		✓	✓		
Visual MLSI Stain Assessment		✓			
Inclusion / Exclusion Criteria		✓	✓		

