3.2 Subgroups/Stratifications

Eligible subjects will be stratified by baseline total MLSI (A×I) score (Low: <45; High: ≥45) and smoking status into four strata in study treatment randomization.

- MLSI Score High (≥45), Smoker
- MLSI Score Low (<45), Smoker
- MLSI Score High (≥45), Non Smoker
- MLSI Score Low (<45), Non Smoker

Subjects identified as being in the wrong strata will be placed in correct strata prior to analysis and will also be considered for protocol deviations and potential exclusion from a PP analysis.

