4.1.3 Analysis Populations

Six populations are defined below.

Population	Definition / Criteria	Analyses Evaluated
All Screened Subjects	All subjects who enter the study and sign the informed consent form. This population includes screen failures as well as those that are randomised	Disposition, AE listing
Randomised	All subjects who are randomised and may or may not receive the application of the study products.	Protocol violations
Safety	All subjects who are randomised and receive at least one dose of investigational product. The Safety population will be reported by treatment received.	Safety analysis
Intent-to-Treat (ITT)	The 'Intent to treat' (ITT) population will include all subjects who are randomised, receive at least one dose of investigational product and have at least one post-baseline efficacy assessment. The ITT population will be reported by randomised treatment.	MLSI analysis
Per-Protocol (PP)	The 'Per-Protocol' (PP) population will include all subjects in the ITT population who have at least one efficacy assessment considered unaffected by protocol deviations. Efficacy assessments considered affected by protocol deviations will be excluded from PP analysis.	MLSI analysis
Repeatability population	All subjects who have an initial and a repeat stain examination at each full MLSI assessment visit.	MLSI repeatability analysis

The primary population for assessment of efficacy will be the ITT population. A PP analysis will be performed on the primary variable (MLSI at week 4) only if more than 20% of the subjects in the ITT population are excluded from the PP population.

The numbers of subjects excluded from each population broken down by the reason for exclusion will be presented ([Table 14.1.3](#)). Subjects excluded from any of the analysis populations will be listed ([Listing 16.2.3.1](#)).

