[1] From ANCOVA with treatment and smoking status as factors and baseline [variable] score as covariate

CCI

207782

Statistical Reporting and Analysis plan, 24 Aug 2017

[2] Difference is first named treatment minus second named treatment such that a negative difference favours the first named treatment

Page x of y

PPD

CCI

207782

Statistical Reporting and Analysis plan, 24 Aug 2017

Protocol 207872

Program Run Date:xxxx

Table 14.2.5.1
Repeatability for MLSI Intensity Score
Repeatability Population

Repeatability Population (N=XX)

Initial \ Repeated	Missing	0	1	2	3
Missing	xx	xx	xx	xx	xx
0	xx	xx	xx	xx	xx
1	xx	xx	xx	xx	xx
2	xx	xx	xx	xx	xx
3	xx	xx	xx	xx	xx
Kappa	0.xx				
95% CI	(0.xx, 0.xx)				

Intensity Score: 0=No Stain; 1=light Stain; 2=Moderate Stain; 3=Heavy Stain. Missing means non-scorable.

Page x of y

PPD

Note to Programmer: For Table 14.2.5.2, use area scoring descriptions in footnote.

CCI

207782

Statistical Reporting and Analysis plan, 24 Aug 2017

Protocol 207872

Program Run Date:xxxx

Table 14.3.1.1
Treatment Emergent Adverse Event by System Organ Class and Preferred Term
Safety Population

Safety Population (N=xx)										
System Organ Class	Test Dentifrice (RDA-58)		Test Dentifrice (RDA-77)		Reference Dentifrice (RDA-80)		Reference Dentifrice (RDA-120)		Overall (N=XX)	
Preferred Term	(N=XX)		(N=XX)		(N=xx)		(N=xx)			
	n (%)	nAE	n (%)	nAE	n (%)	nAE	n (%)	nAE	n (%)	nAE
NUMBER OF SUBJECTS WITH AT LEAST ONE AE	xx (xx.x)	xx	xx (xx.x)	xx	xx (xx.x)	xx	xx (xx.x)	xx	xx (xx.x)	xx
NUMBER OF SUBJECTS WITH NO AE	xx (xx.x)	xx	xx (xx.x)	xx	xx (xx.x)	xx	xx (xx.x)	xx	xx (xx.x)	xx
SKIN AND SUBCUTANEOUS TISSUE DISORDERS	xx (xx.x)	xx	xx (xx.x)	xx	xx (xx.x)	xx	xx (xx.x)	xx	xx (xx.x)	xx
ERYTHEMA	xx (xx.x)	xx	xx (xx.x)	xx	xx (xx.x)	xx	xx (xx.x)	xx	xx (xx.x)	xx
DERMATITIS	xx (xx.x)	xx	xx (xx.x)	xx	xx (xx.x)	xx	xx (xx.x)	xx	xx (xx.x)	xx
GASTROINTESTINAL SYSTEM	xx (xx.x)	xx	xx (xx.x)	xx	xx (xx.x)	xx	xx (xx.x)	xx	xx (xx.x)	xx
ABDOMINAL PAIN	xx (xx.x)	xx	xx (xx.x)	xx	xx (xx.x)	xx	xx (xx.x)	xx	xx (xx.x)	xx
DRY MOUTH	xx (xx.x)	xx	xx (xx.x)	xx	xx (xx.x)	xx	xx (xx.x)	xx	xx (xx.x)	xx
VOMITTING	xx (xx.x)	xx	xx (xx.x)	xx	xx (xx.x)	xx	xx (xx.x)	xx	xx (xx.x)	xx
Etc.										

n (%) = Number (percent) of subjects nAE = Number of adverse events.

Page x of y

PPD

Note to Programmer: For Table 14.3.1.2, change 'System Organ Class' to 'Oral/Non-Oral'

CCI

207782

Statistical Reporting and Analysis plan, 24 Aug 2017

Protocol 207782

Program Run Date:xxxx

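### The repeatability kappa mixes pre- and post-prophylaxis visits, so its rating need not describe the examiner's repeatability at the Week 4 endpoint visit

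*SAP*

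**What the plan says.** SAP 1.1 draws ten subjects for repeat examination in each assessment window, "a total of 30 repeat examinations over the duration of the study) at Visits 2 (pre-prophylaxis), 3 and 4". Between the first window and the other two, prophylaxis takes place and a second examiner confirms that "visible stain (Total MLSI (A×I) = 0), plaque and debris has been removed".

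SAP 4.8 cross-tabulates repeat against original scores for area and for intensity. It plans a Fleiss-Cohen weighted kappa, "along with the 95% CI will be calculated to assess the intra-examiner reliability", and includes every subject with repeatability data. The rating is *excellent* above 0.75, *fair to good* from 0.4 to 0.75 and *poor* below 0.4. The shell of Table 14.2.5.1, titled "Repeatability for MLSI Intensity Score" and reused for area in Table 14.2.5.2, holds one 0-to-3 cross-tabulation, one kappa and one interval. It has no row or column for visit, whereas the MLSI efficacy shells do have a Visit column.

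SAP 4.1.3 defines the Repeatability population as "All subjects who have an initial and a repeat stain examination at each full MLSI assessment visit". Protocol 9.2.1 asks only for an initial and a repeat assessment.

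**The concern.** Kappa compares observed disagreement with the disagreement expected by chance, and the latter grows with the spread of the scores. Subjects enter with visible stain, are cleaned to zero, and are then scored two and four weeks later. If scores are more spread out before cleaning than at Week 4, adding the Visit 2 repeats raises kappa without any better agreement at Week 4.

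Protocol 3.3 gives all stain scoring to one examiner and offers the repeat examinations as the check on that examiner. The primary endpoint is at Week 4. A study report could therefore print a rating that readers take to cover the endpoint visit when it mostly reflects another visit. Separately, a population that needs a repeat at every visit does not match an analysis that includes everyone with repeat data.

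**Working it through.** **The plan's own figure.** 10 subjects × 3 windows = 30 repeat examinations. This reproduces: 10 are pre-prophylaxis and 20 post-prophylaxis.

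**What the documents say about stain levels.** Entry needs only this: "Subjects with a sufficient level of extrinsic dental stain (in the opinion of the examiner) on the facial surfaces". Strata are set as follows: "Eligible subjects will be stratified by baseline total MLSI (A×I) score (Low: <45; High: ≥45) and smoking status". With 12 × 4 = 48 facial sites, 45/48 = 0.94 per site on a 0-to-9 scale, or 45/432 = 10% of the maximum. For the build-up phase, Protocol 3.3 says "we would expect to see little stain build up on the facial surfaces in comparison to the lingual surfaces". No site-score distribution, error rate or expected kappa is given, so everything below rests on assumptions.

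**Formula.** When the two readings have the same distribution, quadratic-weighted kappa is κ = 1 − D/(2V). D is the mean squared difference between readings and V is the variance of a single reading.

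**Model 1: misclassification.** Each reading moves one category with probability e, the same at every visit. Take e = 10% and assumed true scores 0/1/2/3 of 50/25/18/7% at Visit 2, 92/7/1/0% at Week 2 and 85/12/3/0% at Week 4. A site in category 0 or 3 contributes 2 × 0.1 × 0.9 = 0.18 to D, and a site in category 1 or 2 contributes 2 × 0.1 = 0.20.

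| Visit | Mean reading | D | V | κ |
|---|---|---|---|---|
| 2 | 0.863 | 0.189 | 0.913 | 0.90 |
| 3 (Week 2) | 0.182 | 0.182 | 0.177 | 0.49 |
| 4 (Week 4) | 0.265 | 0.183 | 0.270 | 0.66 |

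Pooled:

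- D = (0.189 + 0.182 + 0.183)/3 = 0.184.
- The average within-visit V is (0.913 + 0.177 + 0.270)/3 = 0.453. The variance of the three visit means is 0.092. Together V = 0.545.
- κ = 1 − 0.184/(2 × 0.545) = 0.83.

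Without the between-visit term, κ = 1 − 0.184/(2 × 0.453) = 0.80. So most of the rise from 0.66 comes from the wide spread within Visit 2, and less from the difference between visits. Exact agreement barely differs by visit: 0.9² + 0.1² = 0.82 for an end category and 0.9² + 2 × 0.05² = 0.815 for a middle one.

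Varying the assumptions, with light Week 2 and Week 4 distributions as above:

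| Visit 2 scores 0/1/2/3 (%) | e | Week 4 κ | Pooled κ |
|---|---|---|---|
| 25/25/30/20 | 10% | 0.66 | 0.89 |
| 25/25/30/20 | 20% | 0.48 | 0.80 |
| 50/25/18/7 | 15% | 0.56 | 0.76 |
| 60/25/12/3 | 10% | 0.66 | 0.78 |
| 60/25/12/3 | 15% | 0.56 | 0.69 |

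Over a grid of 36 scenarios, pooled minus Week 4 kappa ran from about 0 (lowest 0.88 − 0.90 = −0.02) to 0.80 − 0.48 = 0.32. The band changed from *fair to good* to *excellent* in 9 of the 36, and in about 15% of 20,000 randomly drawn scenarios. Pooled exceeded Week 4 kappa in about 74% of those draws. In the grid there was no change of band at e = 5%, nor when Week 4 stain resembled the moderate baseline (50/25/18/7%).

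**Model 2: latent stain.** A normal latent stain level (subject SD 0.5, site SD 0.8) plus examiner error is cut into scores 0 to 3, for 10 subjects × 72 sites per visit.

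- Latent visit means 0.8/−1.0/−0.7, error SD 0.5: Week 4 κ 0.61, pooled 0.78. If area equals intensity at each site, this baseline implies a facial total of about 130, nearly three times the cut.
- Baseline lowered to a total of about 45 (latent mean −0.2): Week 4 against pooled is 0.76 and 0.79 at error SD 0.3, 0.69 and 0.72 at 0.4, and 0.62 and 0.66 at 0.5. The excess is 0.03 to 0.04, with no change of band.
- Equal stain at all visits: by-visit and pooled kappa are both about 0.64.

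The two models differ near the cut. The 60/25/12/3% baseline in Model 1 also gives a facial total near 45 if area equals intensity, namely 48 × (0.25 + 0.12 × 4 + 0.03 × 9) = 48, yet the band changes there at e = 10%. The answer depends on the error model as well as on the stain level.

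**The case against.** Four objections have force.

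- **Stain level.** A reader might infer that Visit 2 mouths are heavily stained and that kappa must be inflated by about 0.2. The documents support neither. Entry requires only enough stain in the examiner's opinion, the cut of 45 is about one tenth of the maximum, and the excess near that cut can be as small as 0.03. Likewise, the protocol compares facial with lingual build-up; it does not say that most Week 4 sites score 0 or 1.
- **What the pooled value measures.** It would be too strong to say that it mainly shows the examiner can tell uncleaned from cleaned mouths. Between-visit variance was 0.092/0.545 = 17% of the total in the worked example, about a third in the first latent example and about 7% with baseline near the cut.
- **A Week 4 kappa has its own weakness.** When scores cluster at 0, kappa can be low although readings agree. In the first latent example exact agreement was 77% at Week 4 and 55% at baseline, yet kappa was lower at Week 4 (0.61 against 0.70). Visit 2 repeatability also matters, because that score is the ANCOVA covariate and its facial total sets the stratum. This is why percent agreement belongs beside kappa and the Visit 2 value should stay.
- **Consequence.** SAP 4.8 keeps the repeats out of every efficacy analysis, and no decision depends on the band. This stands in full.

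Pooling is also an inference: no sentence states it, and the list of data displays is redacted. The single coefficient and the shell without a visit dimension still make it the natural reading. Finally, a reader might conclude that the Repeatability population would be empty. That follows only if different subjects are drawn in each window; SAP 4.8's mention of ten subjects could mean the same ten throughout.

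**Conclusion.** The point holds in a limited form. As drafted, the plan yields one kappa for intensity and one for area across visits with very different stain histories. That value can exceed the Week 4 kappa and can fall in a higher band with identical examiner error at every visit. Whether it will, and by how much, cannot be settled from the documents: the excess ranged from about 0 to 0.3 under assumed score distributions and error rates. A change of band needs Week 4 stain clearly lighter than baseline and, in the misclassification model, an error of roughly 10 to 20%.

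The result at risk is the reliability statement. A reader might go further and infer that treatment comparisons are biased or that the examiner is unreliable; nothing in the plan supports either. The population wording in SAP 4.1.3 does conflict with SAP 4.8 and Protocol 9.2.1 and should be corrected in any case. This is a cheap improvement in reporting.

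**What to change.** - In SAP 4.8 and Tables 14.2.5.1 and 14.2.5.2, give the cross-tabulation, weighted kappa and exact percent agreement separately for Visit 2 and for the post-prophylaxis visits (Visits 3 and 4, singly or together).
- Base the reliability statement for the endpoint on the post-prophylaxis value, read alongside percent agreement. Keep the pooled kappa as supplementary.
- In SAP 4.1.3, define the Repeatability population by a repeat at any full MLSI visit, and state in 4.8 that ten subjects are drawn per window.
- Let the interval allow for the clustering of sites within subjects.

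The cost is some SAP wording and one more panel in each of two tables. No new data are needed. The price is wider intervals, because each kappa then uses 10 or 20 repeat examinations instead of 30.

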Attachment 1: List of Data Displays

PPD

Attachment 2: Templates for Tables, Figures and Listings

This is a guideline which will give the guidance of treatment labels that will be used for the table header and in the figures, listings and in the footnotes.

The treatment labels for the column heading will be as follow:

- Test dentifrice (RDA-58)
- Test dentifrice (RDA-77)
- Reference dentifrice (RDA-80)
- Refrence dentifrice (RDA-120)

CCI

207782

Statistical Reporting and Analysis plan, 24 Aug 2017

Protocol 207872

Program Run Date:xxxx

Table 14.1.1
Subject Disposition
All Screened Subjects

All Screened Subjects (N=xxx)

	Test Dentifrice (RDA-58) N (%)	Test Dentifrice (RDA-77) N (%)	Reference Dentifrice (RDA-80) N (%)	Reference Dentifrice (RDA-120) N (%)	Overall N (%)
TOTAL SUBJECTS SCREENED					xxx
SUBJECTS NOT RANDOMISED					xxx (xx.x)
DID NOT MEET STUDY CRITERIA					xxx (xx.x)
ADVERSE EVENT					Xxx (xx.x)
LOST TO FOLLOW UP					xxx (xx.x)
PROTOCOL VIOLATION					Xxx (xx.x)
WITHDRAWAL OF CONSENT					Xxx (xx.x)
OTHER					Xxx (xx.x)
SUBJECTS RANDOMISED	xxx	xxx	xxx	xxx	xxx
COMPLETED STUDY	xxx (xx.x)	xxx (xx.x)	xxx (xx.x)	xxx (xx.x)	xxx (xx.x)
DID NOT COMPLETE STUDY	xxx (xx.x)	xxx (xx.x)	xxx (xx.x)	xxx (xx.x)	xxx (xx.x)
DID NOT MEET STUDY CRITERIA	xxx (xx.x)	xxx (xx.x)	xxx (xx.x)	xxx (xx.x)	xxx (xx.x)
ADVERSE EVENT	xxx (xx.x)	xxx (xx.x)	xxx (xx.x)	xxx (xx.x)	xxx (xx.x)
LOST TO FOLLOW-UP	xxx (xx.x)	xxx (xx.x)	xxx (xx.x)	xxx (xx.x)	xxx (xx.x)
PROTOCOL VIOLATION	xxx (xx.x)	xxx (xx.x)	xxx (xx.x)	xxx (xx.x)	xxx (xx.x)

CCI

207782

Statistical Reporting and Analysis plan, 24 Aug 2017

	Test Dentifrice (RDA-58) N (%)	Test Dentifrice (RDA-77) N (%)	Reference Dentifrice (RDA-80) N (%)	Reference Dentifrice (RDA-120) N (%)	Overall N (%)
WITHDRAWAL OF CONSENT	xxx (xx.x)	xxx (xx.x)	xxx (xx.x)	xxx (xx.x)	xxx (xx.x)
OTHER	xxx (xx.x)	xxx (xx.x)	xxx (xx.x)	xxx (xx.x)	xxx (xx.x)
SAFETY POPULATION	xxx (xx.x)	xxx (xx.x)	xxx (xx.x)	xxx (xx.x)	xxx (xx.x)
ITT POPULATION	xxx (xx.x)	xxx (xx.x)	xxx (xx.x)	xxx (xx.x)	xxx (xx.x)
PP POPULATION	xxx (xx.x)	xxx (xx.x)	xxx (xx.x)	xxx (xx.x)	xxx (xx.x)

Percentages for non-randomised category are based on number of screened subjects; percentages for randomised category are based on number of randomised subjects

Page x of y

PPD

CCI

207782

Statistical Reporting and Analysis plan, 24 Aug 2017

Protocol 207872

Program Run Date:xxxx

Table 14.1.2
Analysis of Population
Randomised Population

Randomised Population (N=xxx)

	Test Dentifrice (RDA-58) N (%)	Test Dentifrice (RDA-77) N (%)	Reference Dentifrice (RDA-80) N (%)	Reference Dentifrice (RDA-120) N (%)	Overall N (%)
SUBJECTS EXCLUDED FROM SAFETY POPULATION	xxx (xx.x)	xxx (xx.x)	xxx (xx.x)	xxx (xx.x)	xxx (xx.x)
REASON 1	xxx (xx.x)	xxx (xx.x)	xxx (xx.x)	xxx (xx.x)	xxx (xx.x)
REASON 2	xxx (xx.x)	xxx (xx.x)	xxx (xx.x)	xxx (xx.x)	xxx (xx.x)
...					
SUBJECTS EXCLUDED FROM ITT POPULATION	xxx (xx.x)	xxx (xx.x)	xxx (xx.x)	xxx (xx.x)	xxx (xx.x)
REASON 1	xxx (xx.x)	xxx (xx.x)	xxx (xx.x)	xxx (xx.x)	xxx (xx.x)
REASON 2	xxx (xx.x)	xxx (xx.x)	xxx (xx.x)	xxx (xx.x)	xxx (xx.x)
...					
SUBJECTS WITH AT LEAST ONE DATA POINT EXCLUDED FROM PP ANALYSIS	xxx (xx.x)	xxx (xx.x)	xxx (xx.x)	xxx (xx.x)	xxx (xx.x)
SUBJECTS COMPLETELY EXCLUDED FROM PP POPULATION	xxx (xx.x)	xxx (xx.x)	xxx (xx.x)	xxx (xx.x)	xxx (xx.x)
PROTOCOL DEVIATIONS LEADING TO EXCLUSION FROM PP					
EXCLUDING ALL					

CCI

207782

Statistical Reporting and Analysis plan, 24 Aug 2017

	Test Dentifrice (RDA-58) N (%)	Test Dentifrice (RDA-77) N (%)	Reference Dentifrice (RDA-80) N (%)	Reference Dentifrice (RDA-120) N (%)	Overall N (%)
DEVIATION 1	xxx (xx.x)	xxx (xx.x)	xxx (xx.x)	xxx (xx.x)	xxx (xx.x)
DEVIATION 2	xxx (xx.x)	xxx (xx.x)	xxx (xx.x)	xxx (xx.x)	xxx (xx.x)
...					
EXCLUDING WEEK2	xxx (xx.x)	xxx (xx.x)	xxx (xx.x)	xxx (xx.x)	xxx (xx.x)
DEVIATION 3	xxx (xx.x)	xxx (xx.x)	xxx (xx.x)	xxx (xx.x)	xxx (xx.x)
DEVIATION 4	xxx (xx.x)	xxx (xx.x)	xxx (xx.x)	xxx (xx.x)	xxx (xx.x)
...					
EXCLUDING WEEK4	xxx (xx.x)	xxx (xx.x)	xxx (xx.x)	xxx (xx.x)	xxx (xx.x)
DEVIATION 5	xxx (xx.x)	xxx (xx.x)	xxx (xx.x)	xxx (xx.x)	xxx (xx.x)
DEVIATION 6	xxx (xx.x)	xxx (xx.x)	xxx (xx.x)	xxx (xx.x)	xxx (xx.x)
...					

Page x of y

PPD

CCI

207782

Statistical Reporting and Analysis plan, 24 Aug 2017

Protocol 207872

Program Run Date:xxxx

Table 14.1.3.1
Subject Demographics and Baseline Characteristics
Safety Population

Safety Population (N=XX)	Test Dentifrice (RDA-58) (N=XX)	Test Dentifrice (RDA-77) (N=XX)	Overall (N=XX)
SEX n (%)				
MALE	xx (xx.x)	xx (xx.x)	...	xx (xx.x)
FEMALE	xx (xx.x)	xx (xx.x)	...	xx (xx.x)
RACE n (%)				
ASIAN	xx (xx.x)	xx (xx.x)	...	xx (xx.x)
BLACK or AFRICAN	xx (xx.x)	xx (xx.x)	...	xx (xx.x)
AMERICAN INDIAN OR ALASKA NATIVE	xx (xx.x)	xx (xx.x)	...	xx (xx.x)
NATIVE HAWAIIAN OR OTHER PACIFIC ISLANDER	xx (xx.x)	xx (xx.x)	...	xx (xx.x)
WHITE	xx (xx.x)	xx (xx.x)	...	xx (xx.x)
MULTIPLE	xx (xx.x)	xx (xx.x)	...	xx (xx.x)
AGE (YEARS)				
n	XX	XX	...	XX
MEAN	XX.X	XX.X	...	XX.X
SD	XX.XX	XX.XX	...	XX.XX
MEDIAN	XX.X	XX.X	...	XX.X

CCI

207782

Statistical Reporting and Analysis plan, 24 Aug 2017

	Test Dentifrice (RDA-58) (N=XX)	Test Dentifrice (RDA-77) (N=XX)	Overall (N=XX)
MINIMUM	XX	XX	...	XX
MAXIMUM	XX	XX	...	XX
STRATIFICATION				
MLSI HIGH, SMOKER	xx (xx.x)	xx (xx.x)	xx (xx.x)	xx (xx.x)
MLSI LOW, SMOKER	xx (xx.x)	xx (xx.x)	xx (xx.x)	xx (xx.x)
MLSI HIGH, NON-SMOKER	xx (xx.x)	xx (xx.x)	xx (xx.x)	xx (xx.x)
MLSI LOW, NON-SMOKER	xx (xx.x)	xx (xx.x)	xx (xx.x)	xx (xx.x)

Page x of y

PPD

CCI

207782

Statistical Reporting and Analysis plan, 24 Aug 2017

Protocol 207872

Program Run Date:xxxx

Table 14.2.1.1.1
Summary of Overall MLSI (AXI) Score
Intent-to-Treat Population

Intent-to-Treat Population (N=XX)

Visit		Test Dentifrice (RDA-58) (N=XX)	TestDentifrice (RDA-77) (N=XX)	Reference Dentifrice (RDA-80) (N=XX)	Reference Dentifrice (RDA-120) (N=XX)	Overall (N=XXX)
Baseline	N	Xx	Xx	xx	Xx	xx
	MEAN	x.xx	x.xx	x.xx	x.xx	x.xx
	SD	x.xxx	x.xxx	x.xxx	x.xxx	x.xxx
	SE	x.xxx	x.xxx	x.xxx	x.xxx	x.xxx
	MEDIAN	x.xx	x.xx	x.xx	x.xx	x.xx
	MINIMUM	X.xx	X.xx	x.xx	X.xx	x.xx
	MaxIMUM	X.xx	X.xx	x.xx	X.xx	x.xx
Week 2	N	Xx	Xx	xx	Xx	
	MEAN	x.xx	x.xx	x.xx	x.xx	
	SD	x.xxx	x.xxx	x.xxx	x.xxx	
	SE	x.xxx	x.xxx	x.xxx	x.xxx	
	MEDIAN	x.x	x.x	x.x	x.x	
	MINIMUM	X.x	X.x	x.x	X.x	
	MAXIMUM	X.x	X.x	x.x	X.x	
Week 4	Same as above					

Page x of y

PPD

CCI

207782

Statistical Reporting and Analysis plan, 24 Aug 2017

Protocol 207782

Program Run Date:xxxx

Table 14.2.1.1.2
Statistical Analysis of Overall MLSI (AXI) Score
Intent-to-Treat Population

Intent-to-Treat Population (N=XX)

Visit	Test Dentifrice (RDA-58) (N=XX)	Test Dentifrice (RDA-77) (N=XX)	Reference Dentifrice (RDA-80) (N=XX)	Reference Dentifrice (RDA-120) (N=XX)
Week 2	LSmean (SE) ^[1]	x.xx (x.xxx)	x.xx (x.xxx)	x.xx (x.xxx)
	Comparison^{[1],[2]}	Difference	95% CI-	P-value
	Test Dentifrice (RDA-58) vs Reference Dentifrice (RDA-80)	x.xx	(x.xx, x.xx)	0.xxxx
	Test Dentifrice (RDA-77) vs Reference Dentifrice (RDA-80)	x.xx	(x.xx, x.xx)	0.xxxx
	Test Dentifrice (RDA-58) vs Reference Dentifrice (RDA-120)	x.xx	(x.xx, x.xx)	0.xxxx
	Test Dentifrice (RDA-77) vs Reference Dentifrice (RDA-120)	x.xx	(x.xx, x.xx)	0.xxxx
	Test Dentifrice (RDA-58) vs Test Dentifrice (RDA-77)	x.xx	(x.xx, x.xx)	0.xxxx
	Reference Dentifrice (RDA-120) vs Reference Dentifrice (RDA- 80)	x.xx	(x.xx, x.xx)	0.xxxx
Week 4	Same as above			

[1] From ANCOVA with treatment and smoking status as factors and baseline [variable] score as covariate

CCI

207782

Statistical Reporting and Analysis plan, 24 Aug 2017

[2] Difference is first named treatment minus second named treatment such that a negative difference favours the first named treatment

Page x of y

PPD

CCI

207782

Statistical Reporting and Analysis plan, 24 Aug 2017

Protocol 207872

Program Run Date:xxxx

Table 14.2.5.1
Repeatability for MLSI Intensity Score
Repeatability Population

Repeatability Population (N=XX)

Initial \ Repeated	Missing	0	1	2	3
Missing	xx	xx	xx	xx	xx
0	xx	xx	xx	xx	xx
1	xx	xx	xx	xx	xx
2	xx	xx	xx	xx	xx
3	xx	xx	xx	xx	xx
Kappa	0.xx				
95% CI	(0.xx, 0.xx)				

Intensity Score: 0=No Stain; 1=light Stain; 2=Moderate Stain; 3=Heavy Stain. Missing means non-scorable.

Page x of y

PPD

Note to Programmer: For Table 14.2.5.2, use area scoring descriptions in footnote.

CCI

207782

Statistical Reporting and Analysis plan, 24 Aug 2017

Protocol 207872

Program Run Date:xxxx

Table 14.3.1.1
Treatment Emergent Adverse Event by System Organ Class and Preferred Term
Safety Population

Safety Population (N=xx)										
System Organ Class	Test Dentifrice (RDA-58)		Test Dentifrice (RDA-77)		Reference Dentifrice (RDA-80)		Reference Dentifrice (RDA-120)		Overall (N=XX)	
Preferred Term	(N=XX)		(N=XX)		(N=xx)		(N=xx)			
	n (%)	nAE	n (%)	nAE	n (%)	nAE	n (%)	nAE	n (%)	nAE
NUMBER OF SUBJECTS WITH AT LEAST ONE AE	xx (xx.x)	xx	xx (xx.x)	xx	xx (xx.x)	xx	xx (xx.x)	xx	xx (xx.x)	xx
NUMBER OF SUBJECTS WITH NO AE	xx (xx.x)	xx	xx (xx.x)	xx	xx (xx.x)	xx	xx (xx.x)	xx	xx (xx.x)	xx
SKIN AND SUBCUTANEOUS TISSUE DISORDERS	xx (xx.x)	xx	xx (xx.x)	xx	xx (xx.x)	xx	xx (xx.x)	xx	xx (xx.x)	xx
ERYTHEMA	xx (xx.x)	xx	xx (xx.x)	xx	xx (xx.x)	xx	xx (xx.x)	xx	xx (xx.x)	xx
DERMATITIS	xx (xx.x)	xx	xx (xx.x)	xx	xx (xx.x)	xx	xx (xx.x)	xx	xx (xx.x)	xx
GASTROINTESTINAL SYSTEM	xx (xx.x)	xx	xx (xx.x)	xx	xx (xx.x)	xx	xx (xx.x)	xx	xx (xx.x)	xx
ABDOMINAL PAIN	xx (xx.x)	xx	xx (xx.x)	xx	xx (xx.x)	xx	xx (xx.x)	xx	xx (xx.x)	xx
DRY MOUTH	xx (xx.x)	xx	xx (xx.x)	xx	xx (xx.x)	xx	xx (xx.x)	xx	xx (xx.x)	xx
VOMITTING	xx (xx.x)	xx	xx (xx.x)	xx	xx (xx.x)	xx	xx (xx.x)	xx	xx (xx.x)	xx
Etc.										

n (%) = Number (percent) of subjects nAE = Number of adverse events.

Page x of y

PPD

Note to Programmer: For Table 14.3.1.2, change 'System Organ Class' to 'Oral/Non-Oral'

CCI

207782

Statistical Reporting and Analysis plan, 24 Aug 2017

Protocol 207782

Program Run Date:xxxx

Table 14.3.1.3
Treatment Emergent Adverse Event by System Organ Class, Preferred Term and Severity
Safety Population

Safety Population (N=xx)

System Organ Class Preferred Term	test ventitric (KDA-58)						...	Overall					
	Mild		Moderate		Severe			Mild		Moderate		Severe	
	n (%)	nAE	n (%)	nAE	n (%)	nAE		n (%)	nAE	n (%)	nAE	n (%)	nAE
NUMBER OF SUBJECTS WITH AT LEAST ONE AE	xx (xx.x)	xx	(xx.x)	xx	xx	xx	...	xx	xx	(xx.x)	xx	xx	xx
SKIN AND SUBCUTANEOUS TISSUE DISORDERS	xx (xx.x)	xx	(xx.x)	xx	xx	xx	...	xx	xx	(xx.x)	xx	xx	xx
ERYTHEMA	xx (xx.x)	xx	(xx.x)	xx	xx	xx	...	xx	xx	(xx.x)	xx	xx	xx
DERMATITIS	xx (xx.x)	xx	(xx.x)	xx	xx	xx	...	xx	xx	(xx.x)	xx	xx	xx
GASTROINTESTINAL SYSTEM	xx (xx.x)	xx	(xx.x)	xx	xx	xx	...	xx	xx	(xx.x)	xx	xx	xx
ABDOMINAL PAIN	xx (xx.x)	xx	(xx.x)	xx	xx	xx	...	xx	xx	(xx.x)	xx	xx	xx
DRY MOUTH	xx (xx.x)	xx	(xx.x)	xx	xx	xx	...	xx	xx	(xx.x)	xx	xx	xx
VOMITTING	xx (xx.x)	xx	(xx.x)	xx	xx	xx	...	xx	xx	(xx.x)	xx	xx	xx

n (%) = Number (percent) of subjects nAE = Number of adverse events.

Page x of y

PPD

CCI

207782

Statistical Reporting and Analysis plan, 24 Aug 2017

Protocol 207872

Program Run Date:xxxx

Listing 16.1.7
Randomisation Information
Randomised Population

Stratum 1: MLSI High, Smoker (Seed: xxxxxx)

Subject Number	Age/Sex/ Race [1]	Randomisation Number	Treatment Randomised	Date of Randomisation
PPD				

* Block size of the study is X.

[1] Age in years; Sex: F = Female, M = Male; Race: A = Asian, B = Black or African American, I = American Indian or Alaska Native, H = Native Hawaiian or Other Pacific Islander, W = White, M = Multiple

Page x of y

PPD

CCI

207782

Statistical Reporting and Analysis plan, 24 Aug 2017

Protocol 207872

Program Run Date:xxxx

Listing 16.2.1.1
Subject Disposition
Randomised Population

Treatment Group: Test Dentifrice (RDA-58)

Subject	Age/Sex/ Race [1]	Screening Date	Treatment Start Date and Time	Date of Completion or Withdrawal	Duration of Treatment (Days)	Completed (Yes/No)	Primary Reason for Withdrawal
PPD							

[1] Age in years; Sex: F = Female, M = Male; Race: A = Asian, B = Black or African American, I = American Indian or Alaska Native, H = Native Hawaiian or Other Pacific Islander, W = White, M = Multiple.

Page x of y

PPD

CCI

207782

Statistical Reporting and Analysis plan, 24 Aug 2017

Protocol 207872

Program Run Date:xxxx

Listing 16.2.1.2
Subject Disposition
Non-Randomised Subjects

Subject Number	Age/Sex/ Race [1]	Screening Date	Reason for Screen Failure
PPD			

[1] Age in years; Sex: F = Female, M = Male; Race: A = Asian, B = Black or African American, I = American Indian or Alaska Native, H = Native Hawaiian or Other Pacific Islander, W = White, M = Multiple.

Page x of y

PPD

CCI

207782

Statistical Reporting and Analysis plan, 24 Aug 2017

Protocol 207656

Program Run Date:xxxx

Listing 16.2.2.1
Major Protocol Deviations
All Randomized Subjects

Treatment Group: XXXXXX

Subject	Sex/Age/ Race [1]	Week(s) Excluded from PP Population	Deviation Reason
---------	-------------------	-------------------------------------	------------------

PPD

[1] Age in years; Sex: F = Female, M = Male; Race: A = Asian, B = Black or African American, I = American Indian or Alaska Native, H = Native Hawaiian or Other Pacific Islander, W = White, M = Multiple.

Page x of y

PPD

CCI

207782

Statistical Reporting and Analysis plan, 24 Aug 2017

Protocol 207872

Program Run Date:xxxx

Listing 16.2.3.1
Exclusion from Analysis Population
Randomised population

Treatment Group: Test Dentifrice (RDA-58)

Subject Number	Age/Sex/Race[1]	Treatment Start Date and Time	Safety Population (Yes/No)	ITT Population (Yes/No)	PP population (Yes/No)
PPD					

[1] Age in years; Sex: F = Female, M = Male ; Race: A = Asian, B = Black or African American, I = American Indian or Alaska Native, H = Native Hawaiian or Other Pacific Islander, W = White, O = Multiple.

Page x of y

PPD

Programming Note for Listing 16.2.3: This listing is based on population definition document.

CCI

207782

Statistical Reporting and Analysis plan, 24 Aug 2017

Protocol 207872

Program Run Date:xxxx

Listing 16.2.4.1
Demographic Characteristics
Randomised Population

Treatment Group: Test Dentifrice (RDA-58)

Subject Number	Age (years)	Sex	Race	Stratification
-------------------	-------------	-----	------	----------------

PPD

Page x of y

PPD

CCI

207782

Statistical Reporting and Analysis plan, 24 Aug 2017

Protocol 207872

Program Run Date:xxxx

Listing 16.2.4.2
Medical History and Current Medical Conditions
Randomised Population

Treatment Group: Test Dentifrice (RDA-58)

Subject	Age/Sex/Race [1]	Any Medical History? (Yes/No)	Medical Condition	Start Date	Ongoing? (Yes/No)	End Date
PPD			xxxxxxxxxxxx	DDMMYYYY	PPD	DDMMYYYY

[1] Age in years; Sex: F = Female, M = Male; Race: A = Asian, B = Black or African American, I = American Indian or Alaska Native, H = Native Hawaiian or Other Pacific Islander, W = White, M = Multiple.

Page x of y

PPD

CCI

207782

